7.4 Post-intervention Period; Long-term Follow-up Phase (1 to 5 Years Post-Transplant)

Outcome data will be collected annually for 5 years post-intervention. However, lung transplantation requires follow-up care for the life of the subject. The hospital where the transplant was performed, or another transplant hospital if the subject moves, will continue providing standard of care follow-up services to the subject for the rest of subject's lifetime.

Visit 8 (Year 2), Visit 9 (Year 3), Visit 10 (Year 4), and Visit 11 (Year 5)

The following data will be collected annually for Year 2 through Year 5 (± 4 weeks) by the Study Center and reported to OPTN/UNOS database and retrieved by the Sponsor (see Section 10.11.2.3):

- Subject and graft survival and if failed, cause of failure
- FEV₁
- Oxygen required at rest
- BOS Grade
- Physical capacity
- Working for income status
- Hospital readmission date/s (if applicable)

7.5 Early Termination Procedures

As lung transplant requires life-long follow-up care from the transplant center, it is unlikely a subject will withdraw from this study post-transplant. Subjects may withdraw consent to participate prior to receiving the intervention (lung transplant) within this study without consequence to the subject or study. In the event that a patient withdraws consent after lung transplant, the following data will be collected by the Study Center either through OPTN and/or SRTR reports or via an early termination visit:

- Subject and graft survival and if failed, cause of failure
- FEV₁
- Oxygen required at rest
- BOS Grade
- Physical capacity
- Working for income status
- Hospital readmission date/s (if applicable)
- Assess AEs

7.6 Unscheduled Visits

Upon receiving any lung transplant, a subject may require a number of unscheduled visits for a variety of reasons, including infection and rejection. If an unscheduled visit is performed due to a documentable AE, then it will be tracked as such. After 30 days post-transplant, all hospital readmissions and root cause will be documented and tracked in the standard OPTN/UNOS database and made available to the Sponsor.

8 QUALITY CONTROL AND ASSURANCE

Quality Management is the overall process of establishing and ensuring the quality of processes, data, and documentation associated with clinical research activities. It encompasses both quality control (QC), and QA activities. All sites conducting research under the sponsorship of the Sponsor are required to have a plan in place for assuring the quality of the research being conducted.

Each site should have standard operating procedures (SOPs) and/or a quality management plan that describe:

- How data will be evaluated for compliance with the protocol and for accuracy in relation to source documents.
- The documents to be reviewed (e.g., CRFs, clinic notes), who is responsible, and the frequency for reviews.
- Who will be responsible for addressing QA issues (correcting procedures that are not in compliance with protocol) and QC issues (correcting errors in data entry).
- Staff training methods and how such training will be tracked.
- If applicable, calibration exercises conducted prior to and during the study to train examiners and maintain acceptable intra- and inter-examiner agreement.

8.1 Sponsor's Quality Process

The Sponsor will conduct the EVLP lung assessment procedure exclusively at the Sponsor's dedicated facility. All post-EVLP procedures will be reviewed by an in-house QA manager for compliance with the TES User Manual and clinical trial protocol, as well as for accuracy in relation to source documents.

In addition, the Sponsor will use an independent CRO to oversee its activities. Finally, Independent Medical Monitors will review all UADE to verify if they are related to the EVLP procedure, the lung transplantation, or other controllable/ uncontrollable event (Section 10.8).

8.2 Training for Study Interventionalists

Training will be completed prior to participation in the clinical trial as outlined in the following sections.

8.2.1 Transplant Center Research Personnel

Study Center site personnel will be trained on study activities, provided a review of Good Clinical Practice (GCP), obtaining informed consent, and the study protocol.

8.2.2 Lung Recovery Surgeons

Surgeons recovering lungs for this study will be experienced lung recovery surgeons listed in the AOPO Credentials Information Network (ACIN).

8.2.3 Lung Transplant Surgeons

All Study Center Investigators will be experienced practitioners of lung transplantation. Current licensure will be maintained in the study records for each participating surgeon.

8.2.4 EVLP Specialists

Ex Vivo Lung Specialists, specifically trained to perform EVLP by University Health Network in Toronto, Canada, will perform all EVLP procedures exclusively at the Sponsor's dedicated site in [name]. Each donor lung, meeting study Inclusion Criteria (Section 5.2) and offered to the Sponsor by a participating transplant center, will be perfused normothermally by the EVLS for up to 6 hours according to the procedures described in the TES User Manual.

All EVLP Specialists performing procedures at the Sponsor's site will have extensive training in the TES through a 6-month in-residence program at TGH, culminating in successful completion of the *Ex Vivo* Lung Specialist Certification and Privileging Exam administered through University Health Network, Toronto, Ontario. This training program is the first of its kind, and the most comprehensive for the newly emerging field of EVLP.

The didactic portion of the EVLS training includes lectures and self-guided reading of applicable medical literature in the following areas:

- a. Lung transplantation- history and overview
- b. Lung allograft donation and procurement
- c. Legislative framework
- d. Lung anatomy and physiology
- e. Perfusion concepts
- f. Ventilation strategies
- g. TES

The practical, hands-on experience includes observing a minimum of five research (animal) EVLP procedures and actively participating in at least 25 research EVLP procedures. Additionally, a minimum of five clinical (human) EVLP procedures will be observed and at least five more clinical cases will be performed with active participation, of which three must be transplanted at the end of the procedure.

The final exam includes written, oral and practical assessments while independently performing a 12-hour long research procedure using the TES to perfuse bilateral swine lungs while being evaluated by a preceptor for the following skills:

- a. Cannulation of the pulmonary artery and left atrium without leaks.

- b. Proper placement and securing of the endotracheal tube correctly in trachea.
- c. Able to discuss equipment used in the TES and rationale for why each piece was specifically chosen.
- d. Calibrate the ventilator, pump flow and pressure sensors independently.
- e. Effectively de-air the perfusion circuit without difficulty.
- f. Place lungs on the EVLP circuit independently without kinks in the cannulas.
- g. Performs retrograde flushing of the lungs prior to perfusion.
- h. Calculates the correct lung flow and ventilation targets.
- i. Warms up lung in correct sequence.
- j. Turns on deoxygenation gas mixture at the correct time and begins ventilation in the correct sequence.
- k. Makes independent changes to the ventilator as required.
- l. Can operate and retrieve data from the Stöckert Centrifugal Pump Console (SCPC) pump, heater/cooler, pressure and temperature monitor, ventilator and ABG machine (see [Appendix 4](#)).
- m. Can perform x-ray and bronchoscopy of the lung independently.
- n. Can maintain a lung on the TES for a minimum of 12 hours without decrease in function.
- o. Can cool down lung in correct sequence.
- p. Can remove lung and repackage independently according to OPTN/UNOS policy.

9 PLANNED STATISTICAL METHODS

9.1 General Considerations

This section describes the planned statistical analyses in general terms. A complete description of the methodology will be specified in a statistical analysis plan (SAP), which will be finalized prior to database lock. Any changes in the statistical methods described in this protocol that occur prior to database lock will be documented in the statistical analysis plan and will not require a protocol amendment.

Statistical analysis will be performed primarily on data collected during the Analysis Phase (1-year post-intervention). The database will be locked for analysis of endpoints after the last subject completes his/her study visit at Year 1, and all queries have been resolved. The Long-term Follow-up data will be summarized when the study has completed in support of long-term evaluation.

No statistical hypotheses will be tested in this study. For ease of presentation, contextual review and statistical programming, the descriptive statistics of the contemporaneous Control group will be presented with those of the EVLP group. Descriptive statistics will be presented as means, standard deviations (SD), medians, and ranges for the continuous variables and as frequencies and percentages for categorical variables. Tabulations will be used to summarize results from descriptive summaries and statistical analyses. A one-sided 95.0% CI will be provided, as appropriate, for the primary endpoints, and two sided 95.0% CI will be presented for all endpoints, as appropriate.

9.2 Determination of Sample Size

In order to provide a sufficient number of subjects for reliable estimation of the primary endpoints, sample size was calculated based on a primary endpoint of PGD3 at T72. Estimates of PGD3 at T72 were based on historical data from EVLP transplant studies where EVLP subjects had rates of PGD3 at T72 ranging from 0% to 15% and conventional transplant subjects ranging from 16.8% to 30% [XVIXO Perfusion Inc. 2014; [name] 2012; [name] 2011a; Machuca 2014; Aigner 2012; Diamond 2013]. Assuming a PGD3 at T72 of 10% and a one-sided 95.0% confidence interval (CI) for a single proportion using the large sample normal approximation adjusted for a finite population of size 2057 (number of lung transplants performed in the US in 2015 [OPTN 2015]), 66 subjects will be needed for the expected upper bound of the CI to not exceed a rate of 16% (nQuery Advisor 7.0, 2007). A total of 66 EVLP subjects and 66 Control subjects will be included in this study.

Rates of 30-day mortality in the EVLP transplant studies have been low, ranging from 3% to 4%. For a sample size of 66, the probability of observing at least one event will be approximately 87% to 93% if the true probability of 30-day mortality is 3% to 4% (nQuery Advisor 7.0, 2007). Subjects will be entered into the study as EVLP transplants occur; however, enrollment to either transplant subtype (single-lung, double-lung) will be limited to 44 subjects to provide a reasonable number of subjects of both subtypes for subgroup examinations.

A contemporaneous Control group will be entered into this study. This Control group will provide context of the EVLP results and estimation of Control group parameters for design of future studies. All analyses of the Control group will be descriptive and no formal statistical comparison will be made between the EVLP and Control groups. As such, the sample size for the Control group will be 66 subjects, and subjects will be matched to the EVLP Group for similarity. Because the ratio of standard lung transplant to EVLP transplant is estimated to be approximately 4:1, it is feasible to obtain a control-EVLP match within the anticipated duration of the study.

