9.5 Primary Endpoint(s)

9.5.1 Primary Graft Dysfunction Grade 3 at 72 hours Post-transplant

The PGD3 Score at 72 hrs post-transplant (T72), as defined in Section 6.7, will be used as the basis for the primary safety endpoint for analysis. The primary endpoint (PGD3 T72) will be calculated from PGD T72 as follows: PGD T72 = {0, 1, & 2} will be coded to PGD3 T72 = 0 and PGD T72 = {3} will be coded to PGD3 T72 = 1.

If a subject dies prior to the T72 measurement, they will be coded to PGD3 T72 = 1. If the T72 value is missing (not collected, not reported, not properly documented), then PGD3 will be coded to PGD3 T72 = 1 for the primary safety analysis.

The primary analysis will be descriptive as the proportion of subjects with PGD3 T72 by Transplant Group (EVLP and Control). A one-sided 95% CI will be calculated around the proportion. A two-sided 95% CI will also be calculated.

There will be no inferential testing conducted.

9.5.2 30-Day Mortality

Subject survival, measured as living or dead, will be recorded for Day 30, Month 6, and Year 1 post-transplant (see Section 6.8). The primary endpoint of 30-Day mortality will be derived as follows: Living at Day 30 will be coded to 0, and Dead before or on Day 30 will be coded to 1. If the vital status of the subject is missing (not collected, not reported, not properly documented), then 30-Day Mortality will remain missing for the primary analysis.

The primary analysis will be descriptive as the proportion of subjects with 30-Day mortality, summarized by Transplant Group. A one-sided 95% CI will be calculated around the proportion. A two-sided 95% CI will also be calculated.

Other supportive endpoints may be provided to supplement the primary analysis, including, but not limited to, median number of days to death and primary cause of death.

Results may be displayed graphically. There will be no inferential testing conducted.

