6.1 Primary Endpoints and Analysis

Primary Graft Dysfunction Score

The PGD3 Score at 72 hours post-transplant (T72) will be used as the basis for the primary safety endpoint for analysis. The primary endpoint (PGD3 T72) will be calculated from PGD T72 as follow: PGD T72 = {0, 1, & 2} will be coded to PGD3 T72 = 0 and PGD T72 = {3} will be coded

to PGD3 T72 = 1.

If a subject dies prior to the T72 measurement, they will be coded to PGD3 T72 = 1. If the T72 value is missing (not collected, not reported, not properly documented), then PGD3 will be coded to PGD3 T72 = 1 for the primary safety analysis.

The subject's PGD Score is to be determined by the Investigator at Baseline (Day 0) after transplantation and upon admission to the ICU, as well as 24, 48, and 72 hours post-transplant.

The primary analysis will be descriptive. The proportion of subjects with PGD3 T72 by Transplant Group (EVLP and Control) will be presented along with a two-sided 95% CI.

There will be no inferential testing conducted.

30-Day Mortality

Subject survival, measured as living or dead, will be recorded for Day 30, Month 6, and Year 1 post-transplant. The primary endpoint of 30-Day mortality will be derived as follows: Living at Day 30 will be coded to 0, and Dead before or on Day 30 will be coded to 1. If the vital status of the subject is missing (not collected, not reported, not properly documented), then 30-Day Mortality will remain missing for the primary analysis.

The primary analysis will be descriptive. The proportion of subjects with 30-Day Mortality by Transplant Group (EVLP and Control) will be presented along with a two-sided 95% CI.

Other supportive endpoints may be provided to supplement the primary analysis, including, but not limited to median number of days to death and primary cause of death.

Results may be displayed graphically. There will be no inferential testing conducted.

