9. SAMPLE SIZE AND POWER CALCULATIONS

In order to provide a sufficient number of subjects for reliable estimation of the primary endpoints, sample size was calculated based on a primary endpoint of PGD3 at T72. Estimates of PGD3 at T72 were based on historical data from EVLP transplant studies where EVLP subjects had rates of PGD3 at T72 ranging from 0% to 15% and conventional transplant subjects ranging from 16.8% to 30%. Assuming a PGD3 at T72 of 10% and a one-sided 95.0% confidence interval (CI) for a single proportion using the large sample normal approximation adjusted for a finite population of size 2057 (number of lung transplants performed in the US in 2015), 66 subjects will be needed for the expected upper bound of the CI to not exceed a rate of 16%. A total of 66 EVLP subjects and 66 Control subjects will be included in this study.

Rates of 30-day mortality in the EVLP transplant studies have been low, ranging from 3% to 4%. For a sample size of 66, the probability of observing at least one event will be approximately 87% to 93% if the true probability of 30-day mortality is 3% to 4%. Subjects will be entered into the study as EVLP transplants occur; however, enrollment to either transplant subtype (single-lung, double-lung) will be limited to 44 subjects to provide a reasonable number of subjects of both subtypes for subgroup examinations.

A contemporaneous Control group will be entered into this study. This Control group will provide context of the EVLP results and estimation of Control group parameters for design of future studies. All analyses of the Control group will be descriptive and no formal statistical comparison will be made between the EVLP and Control groups. As such, the sample size for the Control group will be 66 subjects, and subjects will be matched to the EVLP Group for similarity. Because the ratio of standard lung transplant to EVLP transplant is estimated to be approximately 4:1, it is feasible to obtain a control-EVLP match within the anticipated duration of the study.

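### SAP 9 justifies 66 EVLP subjects by a one-sided 95% upper limit of 16%, but SAP 6.1 reports only a two-sided interval, whose upper limit at a 10% rate is about 17.2%

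*Protocol*

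**What the plan says.** SAP 9 sizes the EVLP group on the first primary endpoint, grade 3 primary graft dysfunction at 72 hours (PGD3): "66 subjects will be needed for the expected upper bound of the CI to not exceed a rate of 16" percent. The derivation is the one in Protocol 9.2, which uses "a one-sided 95.0% confidence interval (CI) for a single proportion using the large sample normal approximation" and is "adjusted for a finite population of size 2057", the count of US lung transplants in 2015.

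The reported interval is set elsewhere. SAP 6.1 states: "The proportion of subjects with PGD3 T72 by Transplant Group (EVLP and Control) will be presented along with a two-sided 95% CI". It says the same for 30-day mortality and mentions no one-sided interval. The SAP revision table records that the one-sided interval was taken out of section 6.1, on the ground that the two-sided one gives the most complete and useful summary. It lists no change to section 9.

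The supplied protocol differs. Protocol 9.5.1 plans both intervals: "A one-sided 95% CI will be calculated around the proportion. A two-sided 95% CI will also be calculated". Protocol 9.1 also says that changes of method made before database lock are documented in the SAP and need no protocol amendment. The SAP's choice therefore governs the analysis.

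**The concern.** Two current sections of the SAP do not fit together. Section 9 promises a precision for an interval that section 6.1 no longer produces. The study tests no hypothesis, so the width of the interval around the PGD3 proportion is what the calculation of n was meant to deliver. Someone who reads SAP 9 and then the results table would expect an upper limit near 16% if the observed rate is about 10%, and would find a higher one.

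A second, smaller matter is the finite-population correction. It is meant for a sample drawn without replacement from the population about which one infers. The 2057 are all US lung transplants of 2015. Under Protocol 5.2.1, EVLP lungs are ones that would not otherwise be used, and under Protocol section 2 the results may serve to plan a future pivotal study. The EVLP subjects are not a sample from the 2057, and the inference is not to that set.

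**Working it through.** **Inputs** (Protocol 9.2, repeated in SAP 9): p = 0.10; target upper limit 0.16, so distance w = 0.06; N = 2057; n = 66. Normal quantiles: 1.645 one-sided, 1.960 two-sided, both at 95%.

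**1. The plan's own figure.**
- Uncorrected size: n0 = z²p(1−p)/w² = 1.645² × 0.09/0.0036 = 67.64.
- Corrected size: n0/(1 + (n0 − 1)/N) = 67.64/(1 + 66.64/2057) = 65.52, rounded up to 66.
- Standard error at n = 66: √(0.09/66) = 0.0369. Correction factor: √((2057 − 66)/2056) = 0.984.
- Upper limit: 0.10 + 1.645 × 0.0369 × 0.984 = 15.98%. The stated figure reproduces.

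**2. The interval in SAP 6.1, by the same approximation.**
- Uncorrected limit at n = 66: 0.10 + 1.960 × 0.0369 = 17.24%.
- With the correction factor: 17.12%.
- Size for a 16% limit: 1.960² × 0.09/0.0036 = 96.04, so 97. With the correction: 96.04/(1 + 95.04/2057) = 91.80, so 92.

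**3. What each change contributes at n = 66.**

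| Interval (normal approximation, at 10%) | With correction | Without | n for 16% (with / without) |
|---|---|---|---|
| One-sided 95% | 15.98% | 16.07% | 66 / 68 |
| Two-sided 95% | 17.12% | 17.24% | 92 / 97 |

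Dropping the correction moves the one-sided limit by 0.10 point and n by 2. Going from one-sided to two-sided without the correction moves the limit by 17.24 − 16.07 = 1.17 points.

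**4. If "expected" means the average over the binomial.** Both documents speak of an expected upper limit. Averaging the uncorrected limit over a binomial with n = 66 and rate 0.10 gives:

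| Method | One-sided 95% | Two-sided 95% |
|---|---|---|
| Normal approximation | 15.94% | 17.07% |
| Wilson | 17.6% | 19.4% |
| Clopper-Pearson | 18.2% | 19.8% |

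The Wilson and Clopper-Pearson rows are assumptions, because SAP 6.1 names no method.

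**5. Results near 10%.** With 66 subjects, 10% is 6.6 events. The two-sided upper limits for the neighbouring counts are:

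| Events | Normal approximation | Wilson | Clopper-Pearson |
|---|---|---|---|
| 6 (9.1%) | 16.0% | 18.4% | 18.7% |
| 7 (10.6%) | 18.0% | 20.3% | 20.6% |

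**The case against.** The strongest reply is that nothing was calculated wrongly and nothing hangs on the figure. The sponsor's inputs give 66. The supplied protocol still plans the one-sided interval, so Protocol 9.2 and 9.5.1 agree with each other. The SAP's change is logged with a reason and Protocol 9.1 permits it. SAP 9 also supports n = 66 by the chance of seeing at least one death within 30 days, which reproduces (1 − 0.97^66 = 86.6%; 1 − 0.96^66 = 93.2%). No hypothesis is tested, and the halting rule for PGD3 uses 50% in the first 10 subjects, not 16%. A two-sided upper limit is the more cautious of the two, so it cannot suggest false safety.

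All of that stands, and it limits the weight of the point. It does not remove the mismatch within the SAP, which remains on either meaning of an expected limit (17.24% or 17.07%, against 16%). The supplied protocol gives its latest amendment as 02 May 2015, while SAP version 2.0 is written against protocol version 6.0 of 03 November 2019, so the two may not be companion versions. The conflict between SAP 9 and SAP 6.1 does not depend on this.

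A reader might also infer that the 16% limit holds only because of the finite-population correction. The documents do not support that. At exactly 10% the uncorrected limit is 16.07%, but averaged over the binomial it is 15.94%, already below 16%. Finally, a sample-size section records how n was chosen, so deleting the correction from that record would misstate the history.

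**Conclusion.** SAP 9 states a precision that the interval in SAP 6.1 does not deliver. At a true rate of 10% and n = 66 the two-sided upper limit is about 17.2% by the normal approximation, some 1.2 points above the stated 16%. It would be about 3.4 points above with Wilson (19.4%) and 3.8 with Clopper-Pearson (19.8%) if one of those were used. Nearly all of the gap comes from the change of sidedness and, where it applies, from the interval method. The finite-population correction is inappropriate in principle but almost without effect.

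Three stronger readings should be resisted:
- *That the sample size contains an arithmetic error.* It does not; it reproduces from its stated inputs.
- *That the study is too small and needs 97 subjects.* No decision, test or stopping rule is tied to 16%. The 97 only shows what the stated limit would cost with a two-sided interval.
- *That the study loses a planned ability to exclude conventional rates.* The lowest conventional rate quoted is 16.8%, which lies between the stated and the delivered limit, but neither document says that 16% was chosen for that reason.

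The figures assume a true rate of 10%, as the plan does.

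**What to change.** Keep n = 66. In SAP 9, add the precision of 66 subjects for the two-sided 95% interval that will be reported, without relying on the finite-population correction: at a true rate of 10%, an upper limit of about 17% by the normal approximation, or the matching figure for the method chosen (about 19.4% for Wilson, 19.8% for Clopper-Pearson). In SAP 6.1, name that method for both primary endpoints. The one-sided derivation with the correction may stay in Protocol 9.2 and SAP 9 if it is marked as the record of how n was chosen.

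This takes a few sentences and no extra subjects. The only cost is a slightly less favourable stated figure.
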